At the start of the session, the parents' progress from the past topic and any other updates will be reviewed and discussed for 5–10 minutes. This is then followed by a 10-minute parent-child play activity. The activity allows the therapist to observe the parent's competency in implementing intervention (i.e. the goals and effective use of strategies) from the previous session's coaching. Based on observations made, the therapist will coach further to strengthen parent's confidence and competency in using strategies to facilitate the attainment of specific learning objectives in the IIP. During the final 10–15 minutes of each session, the therapist will seek feedback from the parent to understand parent's clarity, comfort and confidence in implementing the intervention plan and provide further input and information if required. The therapist will also address any challenges faced or anticipated in the context of implementing the intervention in the home context. The therapist will discuss with parents to implement the intervention plan using at least two play or daily routines (naturally occurring opportunities) identified by the parent. Adult learning principles will be adopted by

the therapist to facilitate active participation in planning and intervention implementation. For clinic-based sessions, an additional 15 minutes is allocated to allow the child and parents to settle down and transit into and out of the therapist's room.

Data collection: For all subjects, video recordings of parent child interactions will be taken at 4 specific time points, namely Baseline, two Midterm reviews and Final review. Specific to the children in the telerehab arm, an additional video recording of parent-child interaction will be done through VC for each on-site review session, totalling 8 video recording time points throughout the program's duration. Recorded videos will be downloaded and transferred to a password encrypted hard drive authorized by the institution data protection and security teams. These recordings can only be accessed by authorized team members with institutional accounts and external raters. They will be used for evaluation on the JERI, NDBI-Fi and for inter-rater reliability assessment.

Parent-delivered therapy (Home-based)

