
g. Is the tele-health intervention more cost-effective than
	
Total direct and indirect costs from health system and societal perspective
	
Total direct and indirect costs from health system perspective: Total intervention costs, including development costs, cost of using the videoconference platform, labour and infrastructure as well as total medical costs and costs of other interventions incurred by parents as related to ASD. Costs related to the evaluation alone will be excluded.
	
Compare total direct and indirect costs from baseline to program conclusion from health system and societal

the standard care?		Total direct and indirect costs from societal perspective: As above and also including cost of travel and productivity losses incurred by parents.	perspective between two intervention groups
h. Is the tele-health intervention effective in improving parents' implementation of intervention strategies?	NDBI (Naturalistic Developmental Behavioural Interventions)-Fi	NDBI-Fi is an 8-item observational rating scheme that evaluates caregiver implementation of common strategies from treatments classified as NDBI based on short videos of caregiver-child interactions.	Change on the NDBI-Fi will be calculated by tracking the changes on individual items and average rating from baseline to program conclusion for participants in the telerehab arm

Quantitative process indicators (the outputs indicated in the logic model) will be assessed in the intervention group as well as part of monitoring and process evaluation.

The qualitative research questions will enhance our understanding of both the impact and process-related outcomes, using semi-structured interview guides. Parents will be asked about perceived effectiveness, engagement and stress, as well as their ability to cope financially with treatment. At baseline, we will also investigate attitudes/perceptions towards telerehab, and factors that affect willingness to take up telerehab. At the end of the study, while the scope of the quantitative evaluation is limited, we will explore parent experiences, satisfaction and concerns, and perceptions of sustainability and future care plans.

Data Collection Plan

Recruitment

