Children who meet the inclusionary criteria will be randomly assigned to the standard or telerehab group of the study. Parents will be informed of the randomisation assignment and clinical diagnostic impression on ADOS. Baseline evaluation measures – Mullen's Scales of Early Learning (MSEL), Vineland Adaptive Behaviour Scales (VABS-III), Parenting Stress

Index (PSI-SF), Joint Engagement Rating Inventory (JERI) and FEIQoL (Families in Early Intervention Quality of Life) - will be completed for all.

Data Collection Time Points

The child and parents' skills will be recorded at 4 data points (baseline; 2 midterm reviews; final review) and progress tracked on the IIP, JERI and FSC. Parent questionnaires will be given at the end of the intervention to evaluate parents' experience with the technology used in the sessions, using a Likert Scale, and to evaluate their experience as *providers* of intervention services to their child. Video analyses will be performed by external raters. Inter-rater reliability will be calculated based on the assessments of raters (number of agreements/number of agreements plus disagreements). Hospital resource use pertaining to the intervention will be recorded at each point as well as healthcare expenditures and household resource use, travel expenses and caregiver time spent.

All clinical data will be collected in the case record form designed for the collection of data for the study. For the various assessment tools that will be used, data will be collected on the assessment tool itself, which will serve as the source of that data.

All data will be later transcribed to excel sheets or other relevant databases as soft data for statistical analysis. The data will be coded to remove any patient identifiers before sharing with the statistician for analysis.

Exit Review for Early Withdrawals

If the participant has completed their first block of intervention and requests to withdraw from the study before their final reviews and assessments (Visit 12 to 14), they will be presented with the option to come back to the clinic for an exit review before withdrawing. In the exit review, the child will be assessed on MSEL, parental stress index, parent satisfaction survey, cost survey, FEIQoL and VABS. Specific to the children in the telerehab arm, an additional video recording of parent-child interaction will be done through VC. However, participants can opt to not come back for the exit review and withdraw from the study immediately.

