Annex 1: Program schedule

Visit no.	Standard program		Telerehabilitation program	
	Test/Intervention	Time (min)	Test/Intervention	Time (min)
ASSESSMENT PHASE				
Visit 0	First Paediatrician visit Screening for ASD (DSM-5) Initiate informed consent taking for study (refer to consent form) – can be done at Visit 0 or 1			30
Visit 1	Second Paediatrician visit Initiate informed consent taking for study (refer to consent form) – can be done at Visit 0 or 1 Refer for ADOS and MSEL if consent is given Otherwise continue with standard care			30
Visit 2-3	Nurse Assessment MSEL + PSI			120
	Psychologist Assessment ADOS + VABS			120
Visit 4	Third Paediatrician visit Paediatrician visit to share Mullen's & ADOS-2 report and confirm enrolment into the study and to inform arm of study. If patient does not meet the inclusion criteria. They will be referred to standard care outside the trial.			30

Visit 5	Therapist Assessment (clinic based)			90
	
 • Foundational Skills Curriculum (FSC) assessment • Parent interview on routines • Joint engagement rating inventory (JERI) • Family Early Intervention Quality of life survey (FEIQoL) • Demographic survey • Cost Survey 			
			Preparation for video conferencing Video conferencing observation (FSC, NDBI-Fi)	30
Visit 6	Parent Education Workshop (Can be conducted either in person or through electronic training slides)			90
For eligible and chosen participants, pre-interview will be conducted between visit 5 and before the Intervention Phase.				45
INTERVENTION PHASE				
1 st block of intervention	Clinic-based intervention (CBI) x 6 (Commencement of Individualised intervention plan (IIP))	60 x 6	Clinic-based intervention (CBI) x 2 (Commencement of Individualised intervention plan (IIP))	60 x 2
			Video conference-based intervention (VCBI) x 4	45 x 4
Parent-delivered therapy home-based)				
2 nd block of intervention	Clinic-based intervention (CBI) x 4	60 x 4	Video conference-based intervention (VCBI) x 4	45 x 4

Visit 7-8	Fourth Paediatrician visit Midpoint Review by paediatrician (clinic based or teleconsultation)			30
	
 • Child's profile, progress • Child and Family's needs • Appropriate recommendations and referrals (if needed) 			
	Midterm Progress Review with Therapist (clinic based)			60
	
 • Foundational skills curriculum – Child's development profile • Joint Engagement Rating Inventory (JERI) • Cost Survey 			

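### Parents' use of strategies (NDBI-Fi) is posed as an effectiveness question but answered with an uncontrolled before-after change in the telerehab arm

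*Combined protocol and SAP*

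**What the plan says.** Row h of the Indicators and Outcomes table asks: "Is the tele-health intervention effective in improving parents' implementation of intervention strategies". The indicator is NDBI-Fi, an 8-item observational rating made "based on short videos of caregiver-child interactions". The expected-change column gives the change in individual items and the "average rating from baseline to program conclusion for participants in the telerehab arm". No comparison with the control arm is mentioned. Rows a to g of the same table each state a comparison between the two groups.

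Other places that bear on row h:

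- **Data collection paragraph (under Intervention: Telerehab Program).** "For all subjects, video recordings of parent child interactions will be taken at 4 specific time points": baseline, two midterm reviews and final review. In the telerehab arm "an additional video recording of parent-child interaction will be done through VC for each on-site review session", making 8 in total. On the use of the recordings it says: "They will be used for evaluation on the JERI, NDBI-Fi and for inter-rater reliability assessment".
- **Annex 1.** NDBI-Fi appears only in the telerehab column, as "Video conferencing observation (FSC, NDBI-Fi)", once at Visit 5 and once at Visits 12-14.
- **Randomisation Process and Blinding.** The list of baseline measures completed for every participant does not include NDBI-Fi.
- **Data Collection Time Points.** "Video analyses will be performed by external raters".
- **Quantitative Outcomes.** Engagement, parental stress and adaptive score are named for between-arm testing. NDBI-Fi is not named.

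**The concern.** A before-after change in one arm contains everything that happens to parents between the two recordings. Annex 2 gives an intervention period of about 40 to 60 weeks in both arms. Over that time parents gain experience with their child and become used to being filmed, and they receive content that is not specific to video conferencing. The control arm gets much of the same content: the same education workshop (Visit 6), therapist coaching over 16 clinic sessions (Intervention: Standard Program), and the same encouragement to spend two hours a week interacting with the child (Randomisation Process and Blinding).

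A rise in NDBI-Fi among telerehab parents would therefore not show that delivery by telehealth produced it, yet row h invites that conclusion. The issue matters because Program Implementation presents video conferencing as a way to build parents' capability in early intervention, and NDBI-Fi is the table's direct rating of how parents carry out the strategies. It is also the only indicator in the table without a control comparison.

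**Working it through.** **1. The plan's own figure.** The documents give no sample size, SD or target effect for NDBI-Fi. The only size calculation is for MSEL (Sample Size Calculation): margin 5, SD 15, expected advantage 1.5, one-sided 5%, 80% power.

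n per arm = 2 × (1.645 + 0.842)² × 15² / (5 + 1.5)² ≈ 65.9, so 66 per arm and 132 in total.

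This reproduces the plan. Below, 66 and the recruitment target of 100 per arm serve only as plausible numbers for NDBI-Fi.

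**2. Is a between-arm NDBI-Fi analysis supplied anywhere?**

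| Place | NDBI-Fi scope |
|---|---|
| Row h | Change in telerehab arm only |
| Annex 1, Visit 5 and Visits 12-14 | Telerehab video-conference observation only |
| List of baseline measures for all | Not listed |
| Quantitative Outcomes | Not named |
| Data collection paragraph | Recordings used for JERI and NDBI-Fi; arm not specified |

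None supplies a comparison. The last can be read as covering recordings from both arms or only the telerehab video-conference clips.

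**3. How far a shared gain could be mistaken for an effect.** Assume that both arms improve by the same amount g, in SD units of the NDBI-Fi change score, so the true between-arm difference is zero. Assume also a two-sided 5% pre-post test in the telerehab arm. The plan states neither g nor this test.

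P(significant) ≈ Φ(g√n − 1.96)

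- n = 66, g = 0.2: Φ(1.62 − 1.96) = 37%
- n = 66, g = 0.3: Φ(2.44 − 1.96) = 68%
- n = 66, g = 0.5: Φ(4.06 − 1.96) = 98%
- n = 100, g = 0.2, 0.3, 0.5: 52%, 85%, over 99%

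A between-arm test at the same level would reject in 5%.

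**4. Would a between-arm comparison be informative?** Detectable difference in SD units of change, two-sided 5%, 80% power, before any gain from baseline adjustment:

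(1.960 + 0.842) × √(2/n)

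- 66 per arm: 0.49 SD
- 80 per arm: 0.44 SD
- 100 per arm: 0.40 SD

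With no NDBI-Fi SD in the documents, these cannot be turned into scale points.

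**5. Rating load.** Baseline and final clinic clips in both arms: 200 participants × 2 = up to 400 clips, each with 8 items. Scoring only the control arm's clips (100 × 2 = 200) would not be enough, because Annex 1 does not schedule the telerehab clinic clips for NDBI-Fi either.

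**The case against.** The strongest reply is that the one-arm scope was chosen. Row h alone drops any reference to standard care, and row h, Annex 1 and the list of common baseline measures agree with one another. The text just after the table says that process indicators are assessed in the intervention group, and a rating of how parents carry out strategies could serve a similar monitoring purpose, although the documents do not label it so. Caregiver behaviour is still compared between arms through JERI (row b). All of this stands. It explains the restriction but does not make a one-arm change an answer to a question about effectiveness.

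Three stronger readings are tempting, and the documents do not support them.

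- A reader might infer that the plan flatly contradicts itself about who is rated. The sentence on the use of the recordings follows a description of both clinic and video-conference clips and does not say that every clip is scored on every tool. It is ambiguous and needs reconciling.
- A reader might infer that a planned randomised comparison was thrown away. No NDBI-Fi comparison was planned.
- A reader might infer a high false-positive rate. Row h states no significance test, and the result follows almost entirely from the assumed gain.

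Two further points stand in part. The workshop and home practice belong to the telerehab programme, so a gain shared by both arms may be real benefit; it just cannot be credited to telehealth delivery. Also, clinic clips show strategy use outside the home, and the plan values the home recording for its natural setting. A clinic-based comparison therefore complements the home clips and does not replace them.

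**Conclusion.** The point holds in limited form. Row h asks about effectiveness and provides only an uncontrolled telerehab change, which cannot separate telehealth delivery from time, repeat filming or content that controls also receive. The restriction looks deliberate.

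The illustrative 37% to 98% at n = 66 rests on an assumed equal gain of 0.2 to 0.5 SD in both arms and on a test that the plan does not state. It shows why attribution fails and does not estimate this trial's error rate. NDBI-Fi is one of several secondary indicators, and the primary MSEL conclusion does not depend on it. This is a minor point that is worth correcting because the minimum correction is free and limits what the trial may claim.

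**What to change.** **Minimum.** Reword row h, and the reporting that follows from it, as a descriptive within-arm change in NDBI-Fi with no claim of effectiveness. This costs nothing beyond the edit.

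**Preferred.** Have the external raters already in the plan score NDBI-Fi on the baseline and final clinic recordings, which exist in both arms. Mask them to arm and time point where possible. Report the between-arm difference with a 95% CI, adjusted for baseline, and describe it as a comparison with standard care. Since no NDBI-Fi margin is set, a difference near zero should not be reported as non-inferiority. Keep the home video-conference clips as a telerehab-only descriptive supplement. The cost is rater time for up to 400 clips at 8 items each; no new filming is needed.

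**In either case.** Reconcile the Data collection paragraph with row h and Annex 1 by stating which recordings, from which arm and at which time points, are scored on NDBI-Fi. Add the chosen analysis to Quantitative Outcomes.

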Patients will be recruited for the program after obtaining a preliminary diagnosis of ASD from the developmental paediatrician. ADOS-2 will be administered to confirm the diagnosis and thus participation in the research study. We will not be advertising this study to the public.

Pilot

An initial pilot feasibility study with 6 children and families will be conducted at the start of the project to identify any practical issues or weaknesses in the program or protocol before full scale evaluation.

Sample Size Calculation

The randomized trial is designed as a non-inferiority study to compare the changes in MSEL between 2 interventions. We expect that the change in MSEL score for the subjects in the new intervention arm will be slightly better than that in the control arm by 1.5 units. Assuming the SD of changes in MSEL score is 15 units, with 5 units as the non-inferiority margin, based on a one-sided test with 80% power and 5% significance level, it is sufficient to recruit 132 subjects (66 in each arm). We decided to recruit 200 subjects in total (100 in each arm) after considering withdrawals and lost to follow up. The computation was performed using a proprietary software programmed in R.

Randomisation Process and Blinding

Computer-generated randomisation will be used to randomly assign the participants to one of the intervention groups. Block randomisation will be used to allocate the recruited subjects into one of the interventions. A randomisation list will be generated by the study statistician and envelopes will be prepared. Although the allocation of intervention will be concealed and the study team will not know in advance which subject will receive which intervention, the blinding will not be possible once the intervention is assigned. Assessors of the initial and final MSEL were not told of the intervention status of the patient to avoid bias in outcome assessment. Blinding of the parents is not possible in the context of this study. Phone calls will be made if necessary to confirm appointments and/or before commencing consultation over video conference in the Telerehab group. Parents in both study arms will be encouraged to spend 2h per week in quality interactions with their children.

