Protocol deviation is defined as any divergence from what was pre-planned and approved by the institutional review board. As the study is conducted as part of routine care and operations, there are practical constraints that may cause protocol deviations to occur. Rescheduling of appointments by the parents (e.g. due to work constraints, child's sickness, other events) or defaulting appointments is inevitable. Hence, for per-protocol analyses, we will only exclude participants with major protocol deviation, which will be defined as participants who do not complete 80% of the intended therapy sessions allocated for their study arm. This means that a control arm participant must attend at least 8 out of 10 clinic-based sessions. For the remaining 2 sessions, participants can either be attending it through video-conferencing (due to the COVID-19 pandemic) or miss the appointment.

Quantitative Outcomes

For the randomized trial, since the study is a non-inferiority study, statistical analysis will be carried out on a per-protocol basis. Subjects with any major protocol deviation as defined above will be excluded from the final analysis.

All demographic, clinical and cost characteristics will be analysed descriptively. Mean (SD) or median (range), whichever is more appropriate will be reported for numerical variables, while N (%) will be reported for categorical variables. 2-sample t-tests, or Mann-Whitney U tests will be used to compare the change of MSEL score between 2 arms. Mean difference and 95% CI will be estimated. If the lower boundary of the 95% CI is more than -5, non-inferiority will be declared. Changes in the quality of parent-child engagement, parental stress index score, and adaptive score will be compared by using either a 2-sample t-test, or a Mann-Whitney U test, whichever is more appropriate. Linear regression will be used to adjust for any covariates.

Cost-Effectiveness Analysis

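### The sample size is built on a one-sided 5% test, but non-inferiority is judged by a 95% confidence interval; at 66 per arm that rule gives about 70% power, not 80%.

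*Combined protocol and SAP*

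**What the plan says.** The Sample Size Calculation section describes a non-inferiority comparison of change in MSEL. Its inputs are:

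- Expected effect: telerehab "will be slightly better than that in the control arm by 1.5 units".
- Variability: "Assuming the SD of changes in MSEL score is 15 units".
- Margin: "with 5 units as the non-inferiority margin".

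From these it concludes that, "based on a one-sided test with 80% power and 5% significance level, it is sufficient to recruit 132 subjects (66 in each arm"). It then raises recruitment to 200 (100 per arm) to cover withdrawal and loss to follow-up, without stating a rate.

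The Quantitative Outcomes section, under Data Analysis Plan, calls for a mean difference with a 95% CI and gives the success criterion: "If the lower boundary of the 95% CI is more than -5, non-inferiority will be declared". The analysis set there is per protocol. Nothing in the document calls this interval one-sided, and a 90% interval is not mentioned.

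**The concern.** Requiring the lower limit of a two-sided 95% interval to lie above the margin is a one-sided test at 2.5%. A one-sided 5% test corresponds to the lower limit of a 90% interval. The trial is therefore sized for one test and decided by a stricter one.

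Two things are at stake. First, a team that relies on the sample-size paragraph would regard 132 evaluable children as enough, when the plan's own rule does not give them 80% power. Second, with two error rates in one plan, some results succeed under one and fail under the other, which invites dispute over the primary conclusion once the data are known.

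**Working it through.** **Inputs**, all from Sample Size Calculation: margin 5; expected difference +1.5 in favour of telerehab; SD of change 15; power 80%; equal allocation. The distance from the expected difference to the margin is 5 + 1.5 = 6.5.

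**Step 1: reproduce the plan's figure.** The number per arm is n = 2(z_α + z_β)² × SD² / 6.5², with z_β = 0.842.

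- One-sided 5%: 2 × (1.645 + 0.842)² × 225 / 42.25 = 65.85, so 66 per arm and 132 in total. This matches the stated figure.
- One-sided 2.5%: 2 × (1.960 + 0.842)² × 225 / 42.25 = 83.60, so 84 per arm and 168 in total. This does not match, so the stated figure was computed at one-sided 5%.

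Using the noncentral t distribution, the two answers become 67 and 85 per arm.

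**Step 2: power at 66 per arm.** SE = 15 × √(2/66) = 2.611, and 6.5 / 2.611 = 2.489.

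- One-sided 5%: Φ(2.489 − 1.645) = 0.801 (0.797 by t).
- 95% CI rule: Φ(2.489 − 1.960) = 0.702 (0.695 by t).

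**Step 3: power under the 95% CI rule at other evaluable numbers.**

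| Evaluable per arm | Normal | t |
|---|---|---|
| 66 | 70.2% | 69.5% |
| 84 | 80.2% | 79.7% |
| 85 | 80.7% | 80.2% |
| 100 | 86.5% | 86.2% |

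**Step 4: loss that 200 recruits can absorb**, taking losses as equal in the two arms.

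- If 132 are needed: 1 − 132/200 = 34%.
- If 168 are needed: 1 − 168/200 = 16%.
- If 170 are needed: 1 − 170/200 = 15%.

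The plan states no attrition rate; 34% is only what its two totals imply.

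**Step 5: results on which the two tests disagree at 66 per arm.** One-sided 5% succeeds if the observed difference exceeds −5 + 1.645 × 2.611 = −0.7. The 95% CI rule needs it to exceed −5 + 1.960 × 2.611 = +0.1. On the plan's assumptions, the chance of landing between these limits is 0.801 − 0.702, about 10%.

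**Step 6: dependence on the assumed advantage.** If the true difference is 0, power at 66 per arm is Φ(5/2.611 − 1.645) = 0.606 at one-sided 5% and Φ(5/2.611 − 1.960) = 0.482 under the 95% CI rule. About 20 points of the fall from 80% to 48% come from dropping the +1.5 assumption, and about 12 from the mismatch.

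**The case against.** **The trial plans 100 per arm, not 66.** This is right as far as it goes: with everyone evaluable, power is 86.5%, and it stays at or above 80% down to 84 or 85 per arm. The 70% describes the number the plan calls sufficient, not full retention. But the smaller allowance must also cover per-protocol exclusions. The 200 is justified only by withdrawal and loss to follow-up, while the Protocol Deviation and Per-protocol Analysis section removes anyone who completes less than 80% of sessions and treats missed appointments as unavoidable. Under Transfer to Early Intervention Programs, study intervention runs for only 10 weeks after EIPIC enrolment, against the 40 to 60 weeks of intervention in Annex 2. The documents give no rates, so a shortfall is possible but not shown.

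**The error is conservative.** This stands. The stricter rule cannot inflate false claims of non-inferiority; the cost is power alone.

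**It is too late to matter.** Version 8 is dated 19/08/2022, and Table 4 schedules no further enrolment in Year 5, which begins in June 2022. If that schedule held, restating the power would not change the number recruited. It would still correct a figure used to judge whether the trial was adequately sized.

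**The interval may have been meant as a one-sided 95% bound.** That would agree with the sample size, but the text does not say so, and an interval reported beside a mean difference is ordinarily two-sided. If a one-sided bound was meant, Quantitative Outcomes needs correcting instead. One of the two sections must change on either reading.

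**Conclusion.** The concern holds. The 66 per arm is correct for the one-sided 5% test it was computed for, but that is not the test that decides the trial. Under the stated decision rule, 66 evaluable per arm gives about 70% power (70.2% normal, 69.5% t), and 80% needs 84 to 85 per arm. The total loss and exclusion that 200 recruits can bear falls from an implied 34% to about 15 to 16%.

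These figures rest on the plan's own SD of 15 and expected advantage of 1.5, on equal losses in the two arms, and on reading the 95% CI as two-sided. The fault is an inconsistency between two sections that misstates power; it does not threaten the type I error.

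**What to change.** Keep the 95% CI rule in Quantitative Outcomes and rewrite the Sample Size Calculation paragraph to match it:

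- State the significance level as one-sided 2.5%, equivalent to the lower limit of a two-sided 95% CI.
- State that 132 evaluable children give about 70% power, and that 168 (84 per arm) are needed for 80%, or 170 (85 per arm) by the t distribution.
- State that 200 recruits allow about 15 to 16% for withdrawal, loss to follow-up and per-protocol exclusion combined, and that power is 86.5% if all are evaluable.

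If the sponsor did intend one-sided 5%, the alternative is to specify the lower limit of a 90% CI in Quantitative Outcomes. This is the weaker choice: it loosens the success criterion late, in a trial that is largely unblinded after allocation and whose timetable includes a preliminary analysis of Year 1 data. It would need documented evidence that it was the intention from the start.

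Either way, one level should appear in both sections before the final analysis. The cost is protocol wording and a less favourable power statement. No recruits beyond 200 are needed as long as 84 to 85 per arm remain evaluable; if fewer remain, the report should give the lower power.
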